##### **7.5.2.3.3 Functional Development**

Functional Development will be assessed by the Bayley Scales of Infant and Toddler Development – Third Edition (Bayley-III). The instrument will be administered at Baseline (Week 0), and at the Week 24 and 48 (or Early Termination) study visits. During the

Continuation Period, the Bayley-III will be completed at 48-week intervals. Bayley-III will not be performed at the ET visit if the assessment was conducted within 1 month of termination.

The Bayley-III ([Bayley 2006](#)) is a standard series of measurements developed to assess the motor (fine and gross), language (receptive and expressive), and cognitive development of infants and toddlers, aged 1 month - 42 months. This measure consists of a series of developmental play tasks and takes between 45 - 60 minutes to administer. The total raw score will be converted into a scaled score and a composite score with percentile rank to compare performance to healthy same-age peers. Unless a child has achieved the highest raw score on the test, the Bayley-III assessments will continue throughout the study to monitor the progress of a child. Additionally, if valid and reliable administration of the instrument is not possible based on the clinical judgment of the Investigator, e.g. language difficulties or clinical condition of the subject, testing may be omitted at that visit.

#### **7.5.2.3.4 Motor Functioning**

A gross motor milestone checklist, developed for use in this trial, will assess gross motor functioning and development. The checklist was designed to allow for assessment of the functional status of the subject requiring limited language interaction and physical handling. See Study Reference Manual for details.

The checklist will be assessed at Baseline (Week 0), and at the Week 24 and 48 (or Early Termination) study visits. During the Continuation Period, the gross motor milestone checklist will be completed at 48-week intervals. The checklist will not be completed at the ET visit if conducted within 1 month of termination.

#### **7.5.2.3.5 Cardiac Ventricular Mass**

Ventricular mass will be assessed by echocardiogram (ECHO) and scored as a z-score relative to normal ventricular mass. Valvular and cardiac function may also be evaluated. An ECHO performed within three months prior to the Baseline visit may be used for the study baseline ECHO provided cardiac ventricular mass can be calculated. ECHO will be performed at the Baseline (Week 0) and Week 48 (or Early Termination) study visits. During the Continuation Period, ECHO will be assessed annually (every 48 weeks).

#### **7.5.2.3.6 Pulmonary Function Testing**

In young patients, traditional pulmonary function testing (i.e. spirometry) is difficult to perform, but measuring pulse oximetry can help assess basic problems in adequate respiration in the youngest patients. Resting O2 saturation will be assessed as a measure of pulmonary function while the subject is breathing room air during the Baseline (Week 0) and Weeks 12, 24, 36, and 48 (or Early Termination) visits. If the subject requires respiratory support, the type and duration should also be noted on the CRF. Pulse oximetry will be assessed every 12 weeks during the Continuation Period.

### **7.5.2.3.7 Biochemical Markers of Bone Turnover**

Biochemical markers of bone turnover (BTMs) will be evaluated as an indicator of changes in bone metabolism in response to UX003 treatment. BTMs in serum include procollagen type 1 N-propeptide (PINP), carboxy-terminal cross-linked telopeptide of type I collagen (CTX-I), bone specific alkaline phosphatase (BALP) and vitamin D. Serum samples will be collected at the Baseline (Week 0) and Week 2, 8, 16, 24, 32, 40 and 48 visits (or Early Termination). Bone turnover markers will be assessed at 24-week intervals during the Continuation Period.

### **7.5.3 Drug Concentration Measurements**

The concentration of rhGUS in the blood will be measured to characterize the PK of UX003 following a single dose and multiple doses. Blood samples for PK analysis will be obtained at Weeks 0 (Baseline), 24, and 48. PK samples will be collected prior to the infusion (pre-dose), 60 minutes after start of infusion, at the end of the infusion, 30-120 minutes post infusion and 4-6 hours post infusion.

Samples may be obtained by separate venipunctures, indwelling catheters, peripherally inserted central catheter (PICC) line or by combinations of these or other suitable methods. The indwelling or PICC line should be managed as prescribed by the clinic procedures. Collection and processing instructions can be found in Laboratory Manual. The same IV line post-infusion end, may be used if the primary line fails, but extensive saline flushing of the line should occur before drawing PK.

### **7.5.4 Safety Measures & General Assessments**

General assessments include medical history, demographics and weight for study drug preparation (Section 7.4.3.2). Safety will be evaluated by the incidence, frequency and severity of AEs and SAEs, including clinically significant changes from study baseline to scheduled time points in vital signs, weight, physical examination, clinical laboratory evaluations, and concomitant medications. To assess the immune response to UX003, the development of IgG antibodies to rhGUS will be evaluated as indicated in the Schedule of Events. Complement C3, C4, and CH50 levels will also be evaluated if a drug-related hypersensitivity reaction is suspected. Refer to the Study Reference Manual for additional details.

To further characterize the disease manifestations, severity and progression of MPS 7, the sponsor aims to determine the specific genetic mutation in each patient enrolled if consent is provided for such testing. This optional assessment can be performed at week 16 or at different time-point if total blood volume at week 16 may exceed maximum allowable volume.

#### **7.5.4.1 Medical History**

A complete medical history will be obtained at the Screening visit. At the Baseline visit, any changes in medical history since Screening will be recorded. General medical information includes subject demographics (date of birth, ethnicity, and sex) and a history of major medical illnesses, diagnoses, and surgeries. Growth history for height and weight will be collected. Pretreatment measurements of height and weight should be collected from the records if possible to assure a pre and post treatment growth rate can be assessed. MPS7 treatment history and relevant concomitant medications will be recorded (start date, stop date, dose, dose regimen). Medications include prescription, over-the-counter, herbal and nutritional supplements. Any relevant concomitant therapy, including physical/occupational therapy will be recorded.

#### **7.5.4.2 Weight**

During the initial 48-week Treatment Period, weight will be obtained at each visit to determine appropriate study drug volume for the subsequent visit, and for safety (refer to Pharmacy Manual for instructions on calculating drug dosage). During the Continuation Period, weight will be obtained at 12-week intervals (in conjunction with anthropometric measurements). Weight will be measured in kilograms using a scale.

#### **7.5.4.3 Physical Examination**

Complete physical examinations will be performed at the Screening, Baseline, Week 12, 24, 36, and 48 study visits (or Early Termination Visit). During the Continuation Period, physical examinations will be conducted at 12-week intervals. Physical examinations will include assessments of general appearance; head, eyes, ears, nose, and throat; the cardiovascular, dermatologic, lymphatic, respiratory, gastrointestinal, genitourinary, neurological, and musculoskeletal systems. If the subject exhibits signs or symptoms of weakness or other new neurological findings, evaluate for cord compression (e.g. reflexes and motor strength).

#### **7.5.4.4 Vital Signs**

Vital signs will include seated systolic blood pressure and diastolic blood pressure measured in millimeters of mercury (mm Hg), heart rate in beats per minute, respiration rate in breaths per minute, and temperature in degrees Celsius (°C). Vital signs measurements will be performed at every visit before any additional assessments are completed. On days when study drug is administered, vital signs will be measured as outlined below.

Week 0 (Baseline) to Week 12, vital signs will be obtained:

- 15 minutes prior to infusion
- Every 15 minutes during the infusion
- Immediately post-infusion

- 15, 30, and 60 minutes post-infusion

Additional measurements should be obtained as appropriate.

Week 14 to Week 240, vital signs will be obtained:

- 15 minutes prior to infusion
- Every 60 minutes for the remainder of the infusion
- Immediately post-infusion
- 60 minutes post infusion

Additional measurements should be obtained as appropriate.

#### 7.5.4.5 Clinical Laboratory Tests for Safety

The clinical laboratory evaluations to be performed in this study are listed in Table 7.5.4.5.1. Clinical laboratory testing for serum chemistry, hematology, and urinalysis will be performed at the Screening, Baseline (Week 0), Week 2, 4, and 8 visits. After Week 8, clinical laboratory evaluations will be performed every 8 weeks until Week 48 (or Early Termination visit). During the Continuation Period, clinical laboratory testing will be performed at 24-week intervals as indicated in the Schedule of Events (Table 2.1). Blood and urine samples will be collected prior to administration of study drug; fasting is not required. See Section 7.4.3.1 for infusion related fasting and refer to the Laboratory Manual for additional details.

**Table 7.5.4.5.1: Clinical Laboratory Assessments for Safety**

Chemistry	Hematology	Urinalysis
Alanine aminotransferase (ALT)	Hematocrit	Appearance
Alkaline phosphatase	Hemoglobin	Color
Amylase	Mean corpuscular hemoglobin (MCH)	pH
Aspartate aminotransferase (AST))	MCH concentration (MCHC)	Specific gravity
Bilirubin (direct and total)	Mean corpuscular volume (MCV)	Ketones
Blood urea nitrogen (BUN)	Platelet count	Protein
Calcium	Red blood cell (RBC) count	Glucose
Chloride	Reticulocyte count	Bilirubin
Creatinine	Neutrophil count (absolute and %)	Nitrite
Gamma-glutamyl transpeptidase (GGT)	Lymphocyte count (absolute and %)	Urobilinogen
Glucose	Monocyte count (absolute and %)	Hemoglobin
Lactate dehydrogenase (LDH)	Eosinophil count (absolute and %)	Creatinine
Phosphorus	Basophil count (absolute and %)	
Potassium	White blood cell (WBC) count	
Protein (albumin and total)	WBC differential	
Sodium		

Subjects who experience a SAE possibly or probably related to study drug or other AE of concern may, at the discretion of the Investigator (and/or medical monitor), have additional blood samples taken for safety laboratory tests.

#### **7.5.4.6 Antibodies to rhGUS**

Prior Phase 3 studies in ERT for MPS have shown that anti-IgG antibodies to the recombinant protein do not have a precise relationship to IARs, but the presence of antibodies may impact on enzyme distribution and efficacy (Dickson et al. 2008). To determine the immunogenicity profile of UX003, testing for IgG antibodies directed against rhGUS will take place at Baseline (Week 0) and the Week 8, 16, 24, 32, 40, and 48 (or Early Termination) visits. During the Continuation Period, anti-drug antibody screening will occur at 12-week intervals. Serum samples for antibodies must be collected before infusion of study drug. For subjects with a positive antibody and/or IAR response, further laboratory evaluation of the immune response to UX003 (i.e. antibodies and complement) may be conducted if warranted.

#### **7.5.4.7 Concomitant Medications**

Concomitant medications will be reviewed and recorded in the subject's CRF at each study visit, beginning at the Screening visit. Medications (investigational, prescription, over-the-counter, and herbal) and nutritional supplements taken during the 30 days prior to Screening will be reviewed and recorded. At each subsequent visit, change in medications since the previous visit will be recorded. A discussion of prohibited and permitted medications is provided in Section 7.4.7.

#### **7.5.4.8 Complement Levels**

Complement components will be assessed to characterize the immune response following a drug-related IAR. For subjects who experience an IAR that is potentially a complement-mediated (anaphylactoid) hypersensitivity reaction, blood samples will be drawn pre- and immediately post-infusion during the subsequent infusion for measurement of the change in C3, C4 and CH50 levels during an infusion. Refer to the Laboratory Manual for additional details on sample processing.

#### **7.5.4.9 Adverse Events**

All AEs will be recorded from the time the subject signs the informed consent until 30 days after the last dose of study drug. The determination, evaluation, reporting, and follow-up of AEs will be performed as outlined in Section 8.5. At each visit subjects will be asked about any new or ongoing AEs since the previous visit. Assessments of AEs will occur at each study visit.

Clinically significant changes from study baseline in physical examination findings, weight, vital signs, and clinical laboratory parameters, will be recorded as AEs or SAEs, if appropriate.

### 7.5.5 Appropriateness of Measures

The primary efficacy variable in this study, uGAG, is a measure of the underlying biochemical defect in MPS 7 patients. Accumulated GAGs and uGAGs are a direct result of the genetic enzyme deficiency state. Based on clinical and nonclinical evidence, uGAG is a direct pathophysiological and readily measured marker of the MPS disease process and a reasonable predictor of treatment effect and clinical benefit. Therefore, if the UX003 restores the underlying biochemical block, a reduction of uGAG is expected.

The additional variables assessed in the program are intended to replicate the clinical assessments used in other MPS ERT programs. The clinical assessments in the study employ standard measures used in other diseases and conditions that impact the respiratory, cardiac, gastrointestinal, skeletal, and central nervous systems. In a multinational study of Laronidase in MPS I patients younger than 5 years, clinical responses in liver size and left ventricular hypertrophy were observed ([Wraith et al. 2007](#)). Pulse oximetry will be conducted to assess respiratory compromise, an important component of disease progression and mortality in MPS 7 subjects. ECHO, ultrasound, and anthropometrics are routine, non-invasive procedures inflicting minimal pain/distress for the subject, while providing relevant indicators of clinical disease phenotype and progression.

The Bayley-III is useful for assessing the compounded impact of multisystem clinical manifestations on the cognitive, motor, and adaptive behavioral development of infants and toddlers. In MPS 7, development in these domains is likely to be affected by the co-morbidities present in these subjects ([McDonald et al. 2010](#)). The Bayley-III may not be reliably administered to all subjects, therefore a motor milestone checklist is also included as an assessment of gross motor functioning and development. The checklist developed for this trial requires limited language interaction or physical handling and allows for a gross motor assessment across all subjects.

Assessments of serum markers of bone formation and bone resorption were included to measure the biochemical markers of bone turnover, which may enable evaluation of the effects of UX003 on skeletal tissue.

Measurements of UX003 drug concentration in blood samples will provide information on relevant PK parameters following a single-dose and at steady-state. Where possible, timing of assessments has been coordinated with standard safety laboratory tests to minimize risk and discomfort and avoid unnecessary sampling.

The safety parameters to be evaluated in this study include standard assessments such as recording of medical history, AEs and SAEs, physical examination, vital signs, serum chemistry and hematology, urinalysis, concomitant medications, and other routine clinical and laboratory procedures. In addition, anti-rhGUS IgG antibody levels and complement C3, C4 and CH50 levels (as indicated) will be determined as a measure of UX003 immunogenicity. Since the study population is comprised of pediatric subjects, age-appropriate safety and efficacy measures have been incorporated into the study design.

## **7.6 Statistical Methods and Determination of Sample Size**

The completeness of the data affects the integrity and accuracy of the final study analysis. Therefore, every effort will be made to ensure complete, accurate and timely data collection, and to avoid missing data. Detailed procedures for handling missing, unused, or spurious data, along with the detailed method for analyses will be presented in the Statistical Analysis Plan (SAP); the information below is intended as a guide to planned analyses.

The statistical analyses will be reported using summary tables, figures, and data listings. All raw data obtained from the CRFs as well as any derived data will be included in data listings. All analyses and tabulations will be performed using SAS®. Descriptive statistics will be used to summarize the data. For continuous variables, the mean, standard error, median, minimum, and maximum will be provided. For categorical variables, the frequency and percent distributions will be provided. Statistical tests will be two-sided at the alpha =0.05 significance level. Two-sided 95% confidence intervals will also be presented when appropriate. The statistical method employed for the analysis of each assessment will be defined in more detail in the SAP.

### **7.6.1 Determination of Sample Size**

Approximately 15 subjects will be enrolled including approximately 5 subjects with hydrops fetalis. Subjects under the age of 5 years at the time of informed consent with a confirmed diagnosis of MPS 7 will be enrolled. Additional subjects previously treated with UX003 under an emergency IND or similar process may also be enrolled at the discretion of the Sponsor. Due to the extremely low prevalence of the disease, the sample size is primarily based on the ability to find qualifying patients.

### **7.6.2 Subject Information**

Subject disposition summaries will include the number of subjects, the number of subjects receiving study medication, the number of subjects completing the study, and the reasons for discontinuation. Demographic variables include age, sex, and race.

### **7.6.3 Populations Analyzed**

The full analysis set will consist of all enrolled subjects who receive at least 1 dose of UX003 during the study.

### **7.6.4 Primary Efficacy Endpoint**

The study is a small open label study to obtain some clinical efficacy data from a small cohort of these ultra-rare patients. A complete hypothesis testing statistical approach is not plausible in this setting, but a reasonable approach to assessing for the biologic efficacy of UX003 will be made.

The primary efficacy analysis will evaluate the mean percent change in uGAG excretion from Week 0 (Baseline) to Week 48 using the generalized estimating equation (GEE) analysis method. For subject(s) previously treated with UX003 under an emergency IND, percent change from initial baseline (prior to first dose of UX003) will be used, if the initial baseline data are available. The null hypothesis of no change in mean uGAG excretion will be tested. An additional analysis will also be performed on the Week 24 time point.

### **7.6.5 Secondary and Tertiary Endpoints and Analyses**

Secondary analysis on growth and hepatosplenomegaly will be evaluated to compare pretreatment with post treatment effects. Growth rate will be compared to historical data obtained from medical history and records (if available), and also compared to published normative data for age and gender. Changes in findings from Baseline for other efficacy variables will be tabulated for each subject. Comparisons of certain efficacy variables with published normative data based on age and gender may also be conducted.

### **7.6.6 Pharmacokinetic Analyses**

The following PK parameters will be calculated from the plasma concentrations of rhGUS measured in these blood samples:

- Area under the plasma concentration-time curve (AUC) from time zero to infinity ( $AUC_{0-\infty}$ )
- AUC from time zero to the time of last measurable concentration ( $AUC_{0-last}$ )
- Maximum plasma concentration ( $C_{max}$ )
- Time to maximum plasma concentration ( $T_{max}$ )
- Elimination half-life ( $t_{1/2}$ )
- Total clearance of drug after IV administration (CL)
- Apparent volume of distribution based upon the terminal phase ( $Vd_z$ )
- Apparent volume of distribution at steady-state ( $Vd_{ss}$ )

### **7.6.7 Safety Analyses**

The primary safety analysis will evaluate the safety of UX003 as measured by the incidence, frequency and severity of AEs and SAEs, including clinically significant changes from study baseline to scheduled time points in:

- Vital signs and weight
- Physical examination findings
- Clinical laboratory evaluations

- Concomitant medications
- IgG antibodies to rhGUS
- Complement C3, C4 and CH50 levels (as indicated)

All AEs will be coded using the Medical Dictionary for Regulatory Activities (MedDRA). The incidence and frequency of AEs will be summarized by System Organ Class (SOC), Preferred Term (PT), relationship to study drug, and severity. No statistical significance will be assessed. A by-subject listing will be provided for those subjects who experience a SAE, including death, or experience an AE associated with early withdrawal from the study or study drug treatment.

Clinical laboratory data will be summarized by the type of laboratory test. The frequency and percentage of subjects who experience abnormal clinical laboratory results (i.e. outside of reference ranges) and/or clinically significant abnormalities after study drug administration will be presented for each clinical laboratory measurement. For each clinical laboratory measurement, descriptive statistics will be provided for study baseline and all subsequent visits. Changes from study baseline to the post-treatment visits will also be provided. Descriptive statistics of vital signs, imaging assessments for safety, and concomitant medications will be provided in a similar manner.

Changes in findings from study baseline physical examinations will be tabulated and listed for each subject by examination category. If there are examination findings that change in more than one subject, these will be tabulated in a separate table and expressed as the number of subjects with the change out of the total.

Anti-drug antibody data will be tabulated over the course of the study. The number of subjects converting to a positive antibody assay value by increasing titer by five-fold over study baseline or more and the time of onset of a positive antibody response will be determined. Descriptive statistics on the titers achieved and the time of onset of the response will be provided (mean, standard deviation, median, range). For subjects with a positive antibody and/or IAR response, further laboratory evaluation of the immune response to UX003 (i.e. antibodies and complement) may be conducted as indicated.

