**Safety Analysis:**

The primary safety analysis will evaluate the safety of UX003 as measured by the incidence and frequency of AEs and SAEs, including clinically significant changes from baseline to scheduled time points in safety parameters. The incidence and frequency of AEs will be summarized by System Organ Class and Preferred Term, relationship to study drug, and severity. No statistical significance will be assessed.

Clinical laboratory data will be summarized by the type of laboratory test. The frequency and percentage of subjects who experience abnormal clinical laboratory results (i.e. outside of reference ranges) and/or clinically significant abnormalities after study drug administration will be presented for each clinical laboratory measurement. For each clinical laboratory measurement, descriptive statistics will be provided for baseline and all subsequent visits. Changes from baseline to the post-treatment visits will also be provided. Descriptive statistics of vital signs, imaging assessments, and concomitant medications will be provided in a similar manner.

Changes in findings from baseline physical examinations will be tabulated and listed for each subject by examination category. If there are examination findings that change in more than one subject, these will be tabulated in a separate table and expressed as the number of subjects with the change out of the total.

Anti-drug antibody data will be tabulated over the course of the study. The number of subjects converting to a positive antibody assay value defined as a titer increase of five-fold or more over baseline, and the time of onset of a positive antibody response will be determined.

Descriptive statistics on the titers achieved and the time of onset of the response will be provided (mean, standard deviation, median, range).

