## 7 INVESTIGATIONAL PLAN

### 7.1 Overall Study Design and Plan

UX003-CL203 is an open-label, multicenter, Phase 2 study to assess the safety and efficacy of UX003 in pediatric MPS 7 subjects. The study seeks to enroll approximately 15 subjects less than 5 years of age at the time of informed consent, and will attempt to include approximately 5 infants with hydrops fetalis if possible. Subjects with prior exposure to UX003 treatment under an emergency IND may also be enrolled at the discretion of the Sponsor. In the initial 48 weeks of treatment, subjects will receive UX003 via IV infusion at a dose of 4 mg/kg QOW. Subjects who complete the 48-week study may choose to continue UX003 treatment in the Continuation Period up to 240 weeks, or until the subject withdraws consent, the subject is discontinued from the study at the discretion of the Investigator or Ultragenyx, or the study is terminated. Figure 7.1.1 provides a schematic of the overall study design.

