## 5 DEFINITIONS

### 5.1 Baseline

- uGAG baseline is defined as the average of all study assessments prior to or on the date of initiation of treatment with UX003 in this study. For subject(s) previously treated with UX003 under an emergency IND, initial baseline will be derived as the average of all assessments prior to or on the date of initiation of the initial treatment with UX003.
- Baseline for growth measurement is defined as the last non-missing study assessment prior to the first dose of UX003. For subject(s) previously treated with UX003 under an emergency IND, the last assessment prior to the initial UX003 treatment may also be used.
- The baseline for echocardiogram: ECHO performed within three months prior to baseline visit may be used as baseline provided cardiac ventricular mass can be calculated.
- Baseline value for other endpoints is the last non-missing study assessment prior to the first dose of UX003 in this study unless otherwise specified.

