## 8 STATISTICAL METHODS OF ANALYSIS

### 8.1 General Principles

Due to the small sample size, all raw data obtained from the Case Report Forms (CRFs) as well as any derived data will be included in data listings or graphs. Descriptive statistics will be used to summarize the data. For continuous variables, means, standard deviations, medians, minimums, and maximums will be provided. For categorical variables, the counts and percentages of subjects in corresponding categories will be provided. All analysis will be based on full analysis set. Statistical tests will be 2-sided at the alpha =0.05 significance level. All p-values will be presented as nominal p-values. Summary statistics will be provided separately for subjects treated with UX003 under an emergency IND or not. Combined summaries will only be provided for uGAG and safety analyses, as prior data to initial treatment will be available for uGAG.

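### Antibody conversion is measured from study baseline, so a child pretreated with UX003 and already positive at Week 0 can be counted as a non-converter

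*Protocol*

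**What the plan says.** **Who may enter.** Protocol 7.1 states: "Subjects with prior exposure to UX003 treatment under an emergency IND may also be enrolled at the discretion of the Sponsor". Protocol 7.6.1 and SAP 3.2 repeat this. Exclusion criterion 3 (protocol 7.3.2) bars recent use of investigational products but exempts UX003, so no gap between earlier UX003 and Week 0 is required.

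**The conversion rule.** Protocol 7.6.7 reports "The number of subjects converting to a positive antibody assay value by increasing titer by five-fold over study baseline or more", with the time of onset and descriptive statistics on the titers reached. The synopsis speaks of subjects "converting to a positive antibody assay value defined as a titer increase of five-fold or more over baseline", without saying which baseline. Protocol 7.5.4.6 takes the first antibody sample at Week 0.

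**The baseline.** For uGAG in emergency-IND subjects, SAP 5.1 says that the "initial baseline will be derived as the average of all assessments prior to or on the date of initiation of the initial treatment with UX003". For growth it allows the last assessment before the initial treatment. Antibodies fall under the general rule: "Baseline value for other endpoints is the last non-missing study assessment prior to the first dose of UX003 in this study unless otherwise specified".

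**Pooling.** SAP 8.1 says: "Summary statistics will be provided separately for subjects treated with UX003 under an emergency IND or not". It continues: "Combined summaries will only be provided for uGAG and safety analyses, as prior data to initial treatment will be available for uGAG".

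**What the SAP plans for antibodies.** SAP 8.8.4 plans a listing of titers and neutralizing antibody by subject and visit. SAP 8.8.3 leaves the summary of IgG antibodies to what is appropriate. Neither mentions the conversion count or time of onset. SAP Section 9 declares no major changes from the analyses in Protocol Amendment 1, and the summary of changes for Amendment 2 lists none to the antibody analysis.

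**The concern.** Conversion is meant to show how many children form antibodies to UX003, and when. That reading needs a reference sample taken before any exposure. For a child treated earlier, the Week 0 sample comes after exposure. If the titer rose during the earlier treatment and then stayed level, the rule finds no five-fold rise, and the child is recorded as not converting.

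The plan recognises this problem elsewhere: it moves the reference point to before the first-ever dose for uGAG and permits the same for growth. It makes no such provision for antibodies, although safety and tolerability form part of the primary objective, and protocol 5.4 names rising antibody titers and infusion-associated reactions as the most common adverse effects of enzyme replacement. The reason SAP 8.1 gives for combining the two groups, that data from before the initial treatment exist, is claimed only for uGAG, yet the combination extends to safety.

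**Working it through.** The documents state no antibody rate, so there is no figure to reproduce. The check has two parts.

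**1. Does the rule misclassify a child?** Apply the five-fold criterion under each reference point:

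- ratio to study baseline = on-study peak / Week 0 titer
- ratio to initial baseline = on-study peak / titer before the first-ever dose

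The titers below are assumed for illustration.

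| Before first-ever dose | Week 0 | On-study peak | Ratio to study baseline | Converter? | Ratio to initial baseline | Converter? |
|---|---|---|---|---|---|---|
| 10 | 10 | 640 | 64 | yes | 64 | yes |
| 10 | 640 | 640 | 1.0 | no | 64 | yes |
| 10 | 640 | 1280 | 2.0 | no | 128 | yes |
| 10 | 640 | 3200 | 5.0 | yes | 320 | yes |
| 10 | 100 | 640 | 6.4 | yes | 64 | yes |

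The first row behaves like a naive child. The rule fails in the second and third rows: positive at entry, then stable or rising less than five-fold. It does not fail in the last two, where a further five-fold rise occurs on study.

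**2. How far could a combined proportion move?** Let N be the number of children, k the number of pretreated children of the kind in rows two and three, and c the number of other converters.

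- by study baseline: c / N
- by initial baseline: (c + k) / N
- shortfall: k / N

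Protocol 7.6.1 gives N as approximately 15; k is not given. The shortfall for one such child is 1/15 = 6.7 points. It is 2/15 = 13.3 points for two and 3/15 = 20.0 points for three. With fewer children enrolled, one child would cost 1/10 = 10.0 points or 1/8 = 12.5 points. If k = 0 the shortfall is zero.

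As an example, assume N = 15, one pretreated child with a stable titer, and 60% conversion among the 14 naive children, which is an expected 8.4 converters. The combined figure is 8.4/15 = 56.0% by study baseline and 9.4/15 = 62.7% by initial baseline. The naive-only figure is 8.4/14 = 60.0%. The emergency-IND row reads 0/1 by study baseline and 1/1 by initial baseline.

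**The case against.** The strongest reply is that SAP 8.1 already requires separate summaries by emergency-IND status, so any antibody summary will show naive children on their own. No document names a combined conversion rate: the protocol asks for a count, and the SAP plans a listing. With about 15 children and all raw data listed or graphed, a reader will see every titer. The plan's own wording, subject(s), allows for a single pretreated child or none.

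Much of this stands, and it rules out several stronger readings that a reader might infer.

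- *That immunogenicity as a whole is understated.* Only the conversion count and the onset time are affected. Titer statistics and the by-subject listing of titers and neutralizing antibody would show the child as positive.
- *That every pretreated child is scored as a non-converter.* A further five-fold rise still counts. The documents do not say that any such child was positive at Week 0, or that earlier treatment ran up to Week 0; titers may have fallen by then.
- *That change-from-baseline safety measures in general should not be pooled.* An argument about titers shows no bias in laboratory values or vital signs, and those are also to be summarised separately.
- *That the Week 0 pharmacokinetic profile is compromised in the same way.* The SAP excludes pharmacokinetics, the synopsis derives the parameters from a population analysis, and a pre-dose sample is drawn. No bias is shown.

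The reply does not repair the rule itself. Separate summaries would still place a positive, previously exposed child in the emergency-IND row as a non-converter, and a listing supplies neither a corrected count nor an onset time. The SAP's silence on the count does not remove the problem either: the protocol promises a figure that the SAP neither defines nor withdraws.

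**Conclusion.** The point holds in a limited form. The conversion rule in protocol 7.6.7, read with SAP 5.1, can count a pretreated, antibody-positive child as a non-converter with no onset time. This requires three things together: UX003 before the study, a positive sample at Week 0, and no further five-fold rise. Each such child lowers a combined proportion by 1/N, 6.7 points at N = 15. That figure depends on the planned enrolment and on a combined proportion being produced at all. The number of such children cannot be found in the documents and may be zero, so no overall bias can be stated. The mechanism is clear from the text; its size is not. A change of wording is justified because it costs almost nothing and removes an error that the separate summaries and listings leave in place.

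**What to change.** In protocol 7.6.7 and SAP 8.8.4:

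- Make conversion and time of onset among treatment-naive children, with their own denominator, the headline figure.
- For pretreated children, measure from the last titer before the first-ever UX003 dose where one exists.
- Where none exists, report the child in a separate row labelled *antibody-positive at study entry after prior UX003*, show any on-study five-fold boost separately, and leave the child out of the combined conversion proportion. Without a pre-treatment sample the response cannot be attributed to UX003, and the label makes no such claim.
- State in the SAP that the conversion count and onset time promised in the protocol will be produced. If they will not be, Section 9 should say so.
- State what value stands for a negative reference sample. SAP 5.4 assigns a titer only after a positive confirmation assay, so a five-fold rise from a negative sample is otherwise undefined.

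No new visits or samples are needed. The cost is a slightly smaller conversion denominator.
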